6.0 PRETREATMENT EVALUATION (To Be Done Day \leq -21; TABLE 4)

- 6.1 Patients will have a complete history and physical examination.
- 6.2 Laboratory studies will include CBC, platelet count, differential count, blood chemistries (SMA 12) (bilirubin, creatinine, albumin, LDH), serum β -2 microglobulin, pregnancy test for women of childbearing potential, bone marrow aspirate (flow cytometry) and biopsy with samples sent for morphology. Hepatitis B (HB) serologies will be performed including HBsAg, HBsAb, and HBcAb. For HBcAb $^+$ (HBsAb $^{+/-}$) individuals, HB virus DNA PCR will be performed.
- 6.3 Prognostic factors will be characterized including immunoglobulin heavy chain variable gene (*IGHV*) family and mutation status; leukemia cell expression of ZAP-70, CD38, and CD49d; thymidine kinase; chromosome abnormalities by FISH (13q del, +12, 11q del, and 17p del); and p53 expression. If bone marrow evaluation is done within 3 months of enrollment, this will not need to be repeated. In these cases, if there is any prognostic factor information missing, this can be obtained from blood. If *IGHV* mutation status and ZAP70 were previously determined at any time, they do not need to be repeated.
- 6.4 Staging CT of chest, abdomen, and pelvis will be done within 2 months of treatment. Any other appropriate radiological and radioisotope examinations should be performed as clinically indicated.
- 6.5 Pretreatment optional blood (20 ml) will be taken to isolate and store mononuclear cells, DNA, RNA, and plasma. Also, pretreatment optional bone marrow will be taken (5 ml) to isolate and store cells, DNA, RNA and marrow plasma. Not all samples will be collected in all patients at all time points.

7.0 EVALUATION DURING STUDY

- 7.1 Monitoring during treatment will consist of weekly (\pm 3 days) blood counts and chemistries (through C1D50), then every 3 months (\pm 2 weeks) during follow-up until alternative treatment for CLL/SLL or death, whichever occurs first. A physician will see patients at least monthly (\pm 5 days) during treatment. A mid-level provider may evaluate patients weekly (\pm 2 days) during treatment (8 weeks) when not seen by the physician.
- 7.2 Follow-up visits will include PE with vital signs, interval history, toxicity/adverse event assessment, CBC with differential, and SMA12. Bone marrow examinations (aspirate, biopsy, and MRD evaluation) will be done at response

assessment (at least 2 months after last dose of ofatumumab) to confirm complete remission, then annually.

- 7.3 Patients will be followed at MDACC for all visits including follow-up, response assessment 3 months after the last ofatumumab dose, and at least annually. Patients will be considered off study when they start alternative treatment for their CLL.
- 7.4 For patients who are HBsAg⁻, HBcAb⁺, HBsAb^{+/-}, and HBV DNA⁻ on enrollment and who proceeded with treatment, HBV DNA PCR testing will be done every 2 months while on treatment, then every 3 months during follow-up for 6 months. Consult with a physician experienced in care and management of subjects with hepatitis B to manage/treat subjects who are anti-HBc positive. Initiate anti-viral therapy if required. If a subject's HBV DNA becomes positive during the study, notify the GSK medical monitor. For subjects who have not completed planned ofatumumab therapy, discuss with the medical monitor the risks and benefits of continuing or discontinuing ofatumumab before appropriate treatment decisions are made for that individual subject.
- 7.5 Information regarding concomitant medications will not be collected for patients on this study. This information is routinely collected and recorded as part of the patient's electronic record. If there is a need to refer to this, it will be available.

The schedule of events is detailed in Table 4.

Table 4. Schedule of Events

Test and Evaluations	Screening Visit Day ≤ -21	C1 D1	C1 D8	C1 D15	C1 D22	C1 D29	C1 D36	C1 D43	C1 D50 (EOT)	C1 D140	FU Q3 MO	ANNUAL FU
Informed consent	X											
Medical history	X											
Interval history, including adverse events and toxicity		X	X ^a	X ^b	X ^c	X ^c						
PE including VS	X	X	X ^a	X ^b	X ^c	X ^c						
Pregnancy test	X											
β2 Microglobulin	X											
Screening BM asp/bx ^d	X											
Zap70, CD38, CD49d, thymidine kinase ^e , IGHV , FISH (13q del, +12, 11q del, and 17p del); and p53 expression ^d		X										
Staging CT of chest, abdomen, pelvis (Day ≤-2 mo)	X											
Hepatitis B surface Ag and surface and core Ab serology	X											
CBC with diff, PLT	X	X	X ^a	X ^b	X ^c	X ^c						
SMA 12	X	X	X ^a	X ^b	X ^c	X ^c						
Ofatumumab		X	X ^a									
For Pts HBsAg ⁻ , HBcAb ⁺ , HBsAb ⁺⁻ , HBV DNA ⁻ on enrollment, HBV DNA PCR testing will be done		X								X ^a	X ^b	X ^c
PK & PD, optional samples	X	X	X ^a	X ^b	X ^c	X ^c						
Response assessment (IWCLL criteria, staging CT scan, and BM for MRD)										X ^b		X ^c

BM=bone marrow evaluation; C=course; D=day; EOT=end of treatment; FU=follow-up; MO=months; PE=physical examination; VS=vital signs; CBC=complete blood count; PK=pharmacokinetic; PD=pharmacodynamic; IWCLL=International Working Group for CLL; MRD=minimal residual disease; ^aindicates ± 3 days; ^bindicates ± 2 weeks; ^cindicates ± 4 weeks; ^dif bone marrow evaluation is done within 3 months of enrollment, this will not need to be repeated. In these cases, if there is any prognostic factor information missing, this can be obtained by blood. If *IGHV* mutation status and ZAP70 were previously determined at any time, they do not need to be repeated. ^ewhen testing is available at MDACC.

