3.0 BACKGROUND DRUG INFORMATION

Ofatumumab FDA-Labeled Indication: refractory chronic lymphoid leukemia

Ofatumumab is currently under development by GlaxoSmithKline for the treatment of relapsed or refractory B-cell follicular lymphoma (FL) for previously untreated FL, for the treatment of relapsed or refractory B-cell chronic lymphocytic leukemia (CLL), for previously untreated CLL and for the treatment of active rheumatoid arthritis and other related autoimmune diseases.

US Trade Name: Arzerra

Dosing & Indications

How Supplied: Intravenous solution, 20 mg/mL

Adult Single-Agent Dosing

- Refractory chronic lymphoid leukemia: 300 mg IV, followed 1 week later by 2000 mg IV weekly for 7 doses (dose 2 to 8), followed 4 weeks later by 2000 mg every 4 weeks for 4 doses (dose 9 to 12); premedicate 30 min to 2 hr

before each dose with acetaminophen (1000 mg or equivalent), oral or IV antihistamine (cetirizine 10 mg or equivalent), and IV corticosteroid (prednisolone 100 mg or equivalent).

- Corticosteroid premedication dose may be gradually reduced for doses 3 through 8, if grade 3 or greater infusion reaction did not occur with the preceding dose.
- Corticosteroid premedication dose may be reduced to prednisolone 50 to 100 mg or equivalent for doses 10 through 12, if grade 3 or greater infusion reaction did not occur with dose 9.
- Initiate dose 1 at an initial rate of 12 mL/hr (3.6 mg/hr), if infusion is well-tolerated, rate may be escalated in 2-fold increments at 30 min intervals to a maximum of 200 mL/hr.
- Initiate dose 2 at an initial rate of 12 mL/hr (24 mg/hr), if infusion is well-tolerated, rate may be escalated in 2-fold increments at 30 min intervals to a maximum of 200 mL/hr
- Initiate (dose 3 through 12) at an initial rate of 25 mL/hr (50 mg/hr), if infusion is well-tolerated, rate may be escalated in 2-fold increments at 30 min intervals to a maximum of 400 mL/hr

Mechanism of Action/Pharmacokinetics

Mechanism of Action

Ofatumumab is a human IgG1-kappa monoclonal antibody that binds to the CD20 molecule on normal B lymphocytes and on B-cell chronic lymphocytic leukemia, resulting in B-cell lysis.

Pharmacokinetics (single-agent in refractory CLL)

- Distribution: 1.7 to 5.1 L
- Excretion: total body clearance, mean: 0.01 L/hr
- Elimination half life: approximately 14 days

Administration/Monitoring

Administration

Intravenous

- Do NOT shake, mix by gentle inversion.
- Do NOT mix ofatumumab with other drugs.

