4. Positive serology for Hepatitis B virus (HB) defined as a positive test for HBsAg. In addition, if negative for HBsAg but HBcAb positive (regardless of HBsAb status), a HB DNA test will be performed and if positive the patient will be excluded.
 - A. Consult with a physician experienced in care and management of subjects with hepatitis B to manage/treat subjects who are anti-HB positive.
5. Pregnant or breast feeding females are not eligible

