5.0 TREATMENT PLAN

This is a single-arm, open label, phase II trial of single-agent ofatumumab.

Patients will receive ofatumumab 300 mg dose 1, then 1000 mg weekly for 7 additional weekly doses (8 doses). All doses will be administered at MDACC. Allopurinol 300 mg PO daily for the first 7 days of course 1 is recommended for tumor lysis prophylaxis.

There are no required prophylactic antibiotics. Herpes virus and PCP prophylaxis may be given at the discretion of the treating physician but is recommended for patients with recent or concurrent corticosteroid use.

Growth factors (neutrophil, erythrocyte, platelet) may be used at the discretion of the treating physician, if clinically indicated.

Pre-medication for each ofatumumab infusion must be given within 30 minutes to 2 hours prior to the infusion:

Table 1. Pre-medication Requirements prior to Ofatumumab Infusions

Infusion #	Acetaminophen (po) or equivalent	Antihistamine (IV or po) diphenhydramine or equivalent	Glucocorticoid (IV) prednisolone or equivalent
1 st	1000 mg	50 mg	50 mg
2 nd	1000 mg	50 mg	50 mg
3 rd -N th	1000 mg	50 mg	0 – 50 mg ¹

1. If the 2nd infusion has been completed without the subject experiencing any grade = 3 AEs, pre-medication with corticosteroid may be reduced or omitted before the 3rd to Nth infusion at the discretion of the treating physician.

First Infusion of 300 mg ofatumumab

The first dose administered of ofatumumab will be 300 mg to minimize infusion reactions. The initial rate of the first infusion of **300 mg** ofatumumab (0.3mg/ml) should be 12mL/h. If no infusion reactions occur the infusion rate can be increased every 30 minutes, to a maximum of 200 mL/h, according to Table 2.

Table 2. Infusion rate at 1st Ofatumumab Infusion

Time	mL/hour
0 – 30 minutes	12
31 – 60 minutes	25
61 – 90 minutes	50
91 – 120 minutes	100
121 – 150+minutes	200

If an infusion reaction develops, the infusion should be temporarily slowed or interrupted. Upon restart, the infusion rate should be half of the infusion rate at the time the infusion was paused. If, however, the infusion rate was 12 mL/hour before the pause, the infusion should be restarted at 12 mL/hour. Hereafter, the infusion rate may be increased according to the judgment of the investigator, in the manner described in this section.

Subsequent infusion of full dose (1000 mg) ofatumumab

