9.0 REMOVAL FROM STUDY

9.1 Progressive or Relapsed Disease

Progressive disease (PD) will be characterized by at least one of the following:

- $\geq 50\%$ increase in the sum of the products of at least two nodes or appearance of new palpable lymph nodes noted on two consecutive examinations at least two weeks apart (at least one node must be ≥ 2 cm).
- $\geq 50\%$ increase in the size of liver and/or spleen as determined by measurement below the respective costal margin; appearance of palpable hepatomegaly or splenomegaly which was not previously present.
- $\geq 50\%$ increase in absolute number of circulating lymphocytes over baseline with $\geq 5,000$ B cells/ μL .
- Transformation to a more aggressive histology (Richter syndrome) documented with biopsy.
- PLT or HGB decrease $\geq 50\%$ from baseline secondary to CLL/SLL.

9.2 Active HBV infection or hepatitis.

9.3 Patient request.

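### The two-monthly HBV DNA PCR interval is longer than the 49-day dosing span, so no scheduled post-exposure result reliably arrives while more than one dose remains

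*Combined protocol and SAP*

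**What the plan says.** **Who is affected.** Section 4.2 excludes HBsAg-positive patients. For those who are HBsAg-negative but HBcAb-positive, "a HB DNA test will be performed and if positive the patient will be excluded". Section 6.2 repeats the screening test: "HB virus DNA PCR will be performed". Patients who are HBcAb-positive and DNA-negative may therefore be treated.

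**On-treatment testing.** For these patients section 7.4 says "HBV DNA PCR testing will be done every 2 months while on treatment, then every 3 months during follow-up for 6 months". It names no visit and no day from which to count.

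**The decision that uses the result.** If HBV DNA turns positive during the study, 7.4 asks for notification of the company's medical monitor, and then: "For subjects who have not completed planned ofatumumab therapy, discuss with the medical monitor the risks and benefits of continuing or discontinuing ofatumumab". Section 9.2 lists as a ground for removal "Active HBV infection or hepatitis".

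**Dosing.** Section 5.0 gives 300 mg, then seven weekly doses of 1000 mg. Table 4 puts the last dose at C1 D50, labelled end of treatment.

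**Table 4.** The schedule has its own row for these patients ("on enrollment, HBV DNA PCR testing will be done"). It marks D1 and three later visits, with windows of ±3 days, ±2 weeks and ±4 weeks in that order. In the extracted text the three later marks sit at D140, the 3-monthly follow-up and the annual follow-up.

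**The concern.** The interval and the regimen do not match. A test repeated every two months cannot fall between the first and last dose of a course that spans seven weeks, unless the count starts well before the first dose or doses are delayed. Yet 7.4 goes on to describe what to do when a patient who still has doses to come turns DNA-positive. That step needs a result from after exposure began, in hand while there is still a dose to withhold.

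The interval would suit a longer regimen. The labelled schedule in section 3.0 adds four doses at 4-week intervals, the first four weeks after dose 8 (50 + 28 = D78). There, a test at D57 to D63 would leave four doses. Here it leaves none.

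At stake is whether a safety rule can work as written, for a complication that section 3.0 says can lead to liver failure and death. No endpoint, sample size or error rate is touched.

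**Working it through.** **Inputs.** Eight weekly doses (section 5.0); last dose at D50 (Table 4); PCR interval of two months (section 7.4); PCR marks in the Table 4 HBV row; screening PCR (section 6.2). Laboratory turnaround is not stated, so it is an assumption, shown at 0, 3, 7 and 14 days.

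**Step 1: the dosing span.** Dose day = 1 + 7 × (dose number − 1), giving D1, 8, 15, 22, 29, 36, 43 and 50. The last is 1 + 7 × 7 = D50, which reproduces Table 4. The span is 50 − 1 = 49 days.

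**Step 2: counting from the D1 test.** Read as 8 weeks, two months gives 1 + 56 = D57. Two calendar months are 59 to 62 days, giving D60 to D63. The test falls 7 to 13 days after the last on-time dose.

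**Step 3: Table 4.** As extracted, the first post-exposure mark is at D140. The more likely intent is D50, D140 and the 3-monthly follow-up, for three reasons. The ±3-day window otherwise goes with weekly treatment visits. The response-assessment row carries the ±2-week window at D140. An annual PCR would also run past the six months that 7.4 sets. On either placement, no PCR is marked from D8 to D43.

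**Step 4: counting from screening.** For a sample drawn L days before D1, the calendar-month test falls on D(60 − L) to D(63 − L). L = 21 gives D39 to D42; L = 10 gives D50 to D53; L = 7 gives D53 to D56. Read as 8 weeks, it falls on D(57 − L): D36 for L = 21 and D50 for L = 7. Section 7.4 does not say to count from screening.

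**Step 5: doses left to withhold.** A dose counts if its day is on or after test day + turnaround.

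| Test | 0 days | 3 days | 7 days | 14 days |
|---|---|---|---|---|
| D1 (before exposure) | 8 | 7 | 7 | 6 |
| Two months from D1 (D57–D63) | 0 | 0 | 0 | 0 |
| D50 mark | 1 | 0 (1 if drawn at D47) | 0 | 0 |
| From screening, L = 21, calendar months (D39–D42) | 2 | 1–2 | 1 | 0 |
| From screening, L = 21, 8 weeks (D36) | 3 | 2 | 2 | 1 |
| From screening, L = 7, calendar months (D53–D56) | 0 | 0 | 0 | 0 |
| Proposed D29, pre-dose | 4 | 3 | 3 | 2 |

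The D1 row leaves plenty of doses, but that sample is taken at first exposure and cannot show reactivation caused by the drug. Among post-exposure tests, only the early-screening count leaves more than one dose, and only at the shorter turnarounds.

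**The case against.** **The plan does name PCR visits.** Section 7.4 names none, but it sits beside Table 4, which has a dedicated row. If the ±3-day mark belongs at D50, the plan is one test at the start and one at the end of a course that 7.1 itself calls eight weeks long. This stands, and the D1 test must be credited. A reader might infer that these patients have no PCR between enrolment and follow-up; the documents do not support that. What remains is that no post-exposure test is named before about D50.

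**The table is damaged.** Its cells are visibly collapsed: the ofatumumab row shows D1 and one further mark for seven more doses. The true position of the HBV marks cannot be recovered from the text, and the shift should not be called an error in the plan. This stands, but the conclusion holds at D50 and at D140.

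**The continue-or-stop sentence has other triggers.** It covers any positive result during the study, including a test ordered by the hepatitis specialist whom 7.4 says to consult. Section 5.0 also allows dose delays; a delay of 7 to 13 days (57 − 50 to 63 − 50) would put the two-monthly test on the day of the last dose. A reader might therefore go too far in calling the sentence a dead letter. But these routes are incidental: none is a scheduled test.

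**No benefit is shown.** The documents give no time to reactivation during treatment, and section 3.0 stresses monitoring for 6 to 12 months afterwards. Antiviral therapy is available however many doses remain. This stands and limits the severity.

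**Conclusion.** The concern holds in a narrow form. In an HBcAb-positive, DNA-negative patient dosed on time, no scheduled post-exposure PCR reliably gives a result while more than one of the eight doses remains. The D50 mark, the most favourable likely placement in Table 4, leaves one dose with a same-day result and none at a 7-day turnaround. The two-monthly count from D1 leaves none. An early screening sample, a dose delay or an unscheduled test could do better, but only incidentally.

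Severity is minor. Specialist consultation, antiviral therapy, medical-monitor notification, weekly chemistries, removal under 9.2 and follow-up PCR all remain, although the chemistries do not measure HBV DNA.

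A reader might infer that patients would come to harm from the gap, or might turn doses into modelled drug exposure to put a size on it. The documents support neither. They do not say how many of the at most 44 patients would be HBcAb-positive (possibly none), nor what an earlier result would prevent. Doses left to withhold measures opportunity, not harm avoided.

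The result rests on on-time dosing, the stated turnaround assumptions and an uncertain column position in Table 4.

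**What to change.** In section 7.4 and the Table 4 HBV row, replace the two-monthly on-treatment interval with a PCR at a named mid-course weekly visit plus one at D50 (end of treatment). Keep the D1 test and the 3-monthly follow-up tests.

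D29 pre-dose is an example. It follows four doses and leaves three to withhold at an assumed 7-day turnaround, or two at 14 days. Any named visit that still leaves doses to withhold at the local turnaround would serve.

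The cost is an amendment to one sentence and one table row, and one or two extra PCR tubes per HBcAb-positive patient (one if the D50 test is already intended). Blood is already drawn at those visits for weekly counts and chemistries.

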8.0 RESPONSE CRITERIA AND TOXICITY EVALUATION

Responses will be assessed according to the 2008 IWCLL guidelines (Table 5)⁷ at MDACC. Responses will be evaluated by physical examination; CBC; CT of chest, abdomen, pelvis; and for individuals in complete remission bone marrow aspirate and biopsy with evaluation of residual disease (MRD) by 4-color flow cytometry at least 3 months after completing ofatumumab.

Table 5. 2008 IWCLL Response Assessment

SITE	CR	PR
Nodes*†	None > 1.5 cm	Decrease ≥ 50%
Liver/Spleen	Not palpable	Decrease ≥ 50%
Symptoms	None	N/A
PMN	>1,500/µL	N/A
Platelet count	> 100,000/µL	>100,000/µL or increase ≥ 50% over baseline
Hemoglobin (untransfused)	>11.0 g/dL	>11.0 g/dL or increase ≥ 50% over baseline
Blood Lymphocytes	<4,000/µL	Decrease ≥ 50%
Bone Marrow Aspirate**	Normocellular <30% lymphocytes	> 50% decrease in marrow infiltrate or B lymphoid nodules
Biopsy	No lymphocyte infiltrate or nodules	

* CT scan of neck, chest, abdomen, and pelvis to confirm CR is recommended.

† Sum of the product of multiple lymph nodes.

** Evaluation for MRD will be performed either by 4-color flow cytometry or by molecular evaluation.

N/A=not applicable

Non-hematologic toxicity will be assessed, summarized and graded according to the Common Terminology Criteria for Adverse Events (CTCAE) Version 4.0. Hematologic toxicity will be assessed, summarized and graded according to the 2008 IWCLL Guidelines (Table 6).

8.1 ADVERSE EVENT DOCUMENTATION

Adverse events will be documented in the medical record and entered into the case report form (CRF) according to the Leukemia –Specific Adverse Event Recording and Reporting Guidelines (Appendix E). PDMS/Core will be used as the CRF report form for this protocol. The Investigator or physician designee is responsible for verifying and providing source documentation for all adverse events and assigning the attribution for each event for all subjects enrolled on the trial. The Investigator will sign and date the PDMS CRF toxicity pages for each patient at the completion of each course. Following signature, the CRF will be used as source documentation for the adverse events attribution.

Table 6. 2008 IWCLL Grading for Hematological Toxicity

Grade	Decrease in PLT* or HGB** (nadir) from pretreatment value, %	Absolute neutrophil count (ANC)/ μ l*** (nadir)
0	$\leq 10\%$	≥ 2000
1	11 – 24%	$\geq 1500 - < 2000$
2	25 – 49%	$\geq 1000 - < 1500$
3	50 – 74%	$\geq 500 - < 1000$
4	$\geq 75\%$	< 500

Death occurring as a result of toxicity at any level of decrease from pretreatment will be recorded as grade 5.

* PLT counts must be below normal levels for grades 1-4. If, at any level of decrease, the PLT count is $< 20K/\mu\text{L}$, this will be considered grade 4 toxicity, unless there was severe or life-threatening low initial PLT count ($< 20K/\mu\text{L}$) pretreatment, in which case the patient is not evaluable for toxicity referable to PLT count.

** HGB levels must be below normal levels for grades 1-4. Baseline and subsequent HGB determinations must be performed before any given transfusions.

*** If the absolute neutrophil count (ANC) reaches $<1000/\mu\text{L}$, it should be judged to be grade 3 toxicity. If the ANC was $<1000/\mu\text{L}$ before therapy, the patient is not evaluable for toxicity referable to the ANC.

9.0 REMOVAL FROM STUDY

9.1 Progressive or Relapsed Disease

Progressive disease (PD) will be characterized by at least one of the following:

- $\geq 50\%$ increase in the sum of the products of at least two nodes or appearance of new palpable lymph nodes noted on two consecutive examinations at least two weeks apart (at least one node must be ≥ 2 cm).
- $\geq 50\%$ increase in the size of liver and/or spleen as determined by measurement below the respective costal margin; appearance of palpable hepatomegaly or splenomegaly which was not previously present.
- $\geq 50\%$ increase in absolute number of circulating lymphocytes over baseline with $\geq 5,000$ B cells/ μL .
- Transformation to a more aggressive histology (Richter syndrome) documented with biopsy.
- PLT or HGB decrease $\geq 50\%$ from baseline secondary to CLL/SLL.

9.2 Active HBV infection or hepatitis.

9.3 Patient request.

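### Progression is listed as a reason for removal from study (Section 9.1), while Sections 7.1 and 7.3 follow patients to next CLL therapy; the sections need reconciling to protect time to next therapy (minor)

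*Combined protocol and SAP*

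**What the plan says.** Section 9 of the combined protocol and SAP is headed "9.0 REMOVAL FROM STUDY". Its first entry is "9.1 Progressive or Relapsed Disease", followed by "9.2 Active HBV infection or hepatitis" and "9.3 Patient request". Under 9.1 there is only a definition, introduced by "Progressive disease (PD) will be characterized by at least one of the following". No sentence there says whether follow-up or data collection stops or continues.

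Section 7 has the explicit follow-up sentences. Section 7.1 schedules three-monthly monitoring "during follow-up until alternative treatment for CLL/SLL or death, whichever occurs first". Section 7.3 states: "Patients will be considered off study when they start alternative treatment for their CLL". Neither mentions progression.

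Three other places bear on this:

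- Section 1.0 makes time to next chemoimmunotherapy or other therapy secondary objective 2.
- Section 2.0 gives delay of first chemoimmunotherapy as the overall aim, to be assessed by an observed/expected (O/E) ratio built from the institution's CLL database.
- Section 10.0 plans Kaplan-Meier estimates, naming only overall survival (OS) and event-free survival, and gives no censoring rules.

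**The concern.** The document gives two different events that end participation: progression (9.1) and the start of another CLL treatment (7.3). For time to next therapy the choice matters. A patient who has progressed is more likely than others to start therapy soon, so ending observation at progression removes from the risk set the patients closest to the event. That is informative censoring. It makes time to next therapy look longer and lowers the observed count in the O/E ratio, both in favour of ofatumumab.

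A smaller, separate gap concerns OS. Sections 7.1 and 7.3 end follow-up at next therapy, and no section collects vital status after that. The only later contact described is reporting of treatment-related serious adverse events (Section 13.0). An OS curve would therefore be censored at next therapy, which is informative if the death hazard changes afterwards.

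**Working it through.** **1. Can both texts be followed as written?** Reading Section 9 as stopping treatment only would remove the conflict, but it leaves 9.1 with little to do. Treatment is eight weekly doses ending on day 50 (Section 5.0, Table 4), and the historical medians in Section 2.0 are 27 months (treatment failure, N=34) and 43 months (progression in responders, N=28). Most progressions would fall after treatment has ended.

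**2. Are progression and next therapy separate events here?** Yes. Section 9.1 counts new palpable nodes with at least one of 2 cm or more, or a lymphocyte rise of 50% or more with at least 5,000 B cells/µL and no time limit. The treatment indications listed in Section 4.2 include nodes above 10 cm, or a 50% lymphocyte rise within 2 months. A patient can progress without meeting such an indication, and in that interval removal could lose the therapy date.

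**3. The plan's own figures.** None is given for this endpoint. The only design calculation, for the complete response rate, reproduces (alpha 0.0953, power 0.8003, early termination 0.3286 against the stated 0.33) and does not depend on this point.

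**4. Illustration if 9.1 is literal and no later dates are obtained.** From the documents: medians of 27 and 43 months, N=44. Assumed: exponential times; the quoted medians taken as time to the first of progression or therapy; a mean lag m of 6 to 24 months from progression to therapy; and a share f of first events that are therapy starts recorded at or before removal. Horizon T = 60 months.

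- Rate: l = ln 2/27 = 0.02567 per month (ln 2/43 = 0.01612).
- True proportion without next therapy: S(T) = exp(−lT) + (1−f)·l·[exp(−lT) − exp(−T/m)]/(1/m − l).
- Kaplan-Meier censored at progression: exp(−f·l·T).

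Example, 27 months, f = 0.5, m = 12: S = 0.2143 + 0.5 × 0.02567 × (0.2143 − 0.0067)/(0.0833 − 0.0257) = 0.261. Censored curve = exp(−0.770) = 0.463. Bias = 20 points.

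| f | Bias, 27 months (points) | Bias, 43 months (points) | Starts recorded / true, of 44 (27 months) | Observed count / true |
|---|---|---|---|---|
| 10% | 45–61 | 36–49 | 3.5 / 26–33 | 0.10–0.13 |
| 20% | 35–49 | 29–41 | 6.9 / 27–33 | 0.21–0.26 |
| 50% | 14–23 | 14–22 | 17.3 / 30–34 | 0.51–0.58 |
| 80% | 3.5–7.0 | 4.4–7.3 | 27.7 / 33–34 | 0.81–0.85 |
| 90% | 1.4–3.2 | 2.0–3.5 | 31.1 / about 34 | 0.90–0.92 |

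Recorded starts are 44·f·(1 − exp(−lT)); true starts are 44·(1 − S). Counts are omitted for 43 months because that median is for responders only. Adding deaths at an assumed 2% per year and administrative censoring at 36 to 84 months changes each bias by about 0.1 point.

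A second set of assumptions gave 6 to 50 points at 36 months: median lags of 6 to 24 months, and 0%, 25% or 50% of patients starting therapy at progression. The direction was the same throughout.

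**5. The O/E ratio is not the observed count.** Section 2.0 does not say how expected events accrue. If they also stop at removal, and the true hazard is taken as expected, expected events per patient are ∫₀ᵀ l·exp(−ls)·[−ln S(s)] ds + exp(−lT)·[−ln S(T)]. With 27 months, m = 24 and f = 0.5, this gives 24.0 expected events in 44 patients, so O/E = 17.3/24.0 = 0.72, against an observed-count fraction of 0.58. At f = 0.8 it is 0.92 against 0.85.

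**6. OS.** With an assumed death hazard of 2% per year before therapy, the curve censored at next therapy reads exp(−0.02 × 5) = 90.5% at 5 years. Truth, over both medians, f from 0 to 0.9 and m of 6 and 24 months, is 90.5% if the hazard is unchanged after therapy, 84–88% if it becomes 5% per year, and about 75–84% at 10% per year.

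**The case against.** The strongest reply is that the conflict is between a heading and two operative sentences. Section 9.1 never states that follow-up stops, while 7.1 and 7.3 say expressly when it does. Specific text would normally govern, and then the bias is zero. Section 7.4 also treats a patient whose HBV DNA turns positive as a question of continuing or discontinuing the drug, which suggests that Section 9 may be about treatment. This carries weight and limits the point to a conditional one. It does not remove it, because the heading says study and the treatment-only reading leaves 9.1 almost empty.

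The harm also needs a second condition: that dates are not obtained after removal. Section 7.3 says "Patients will be followed at MDACC for all visits including follow-up", and the planned comparison uses the institution's own database, so total loss is a worst case. That stands too, although no section requires the date after removal. Partial recovery is not modelled above.

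A reader might infer that the protocol does remove patients at progression, and that a planned Kaplan-Meier analysis of this endpoint is inflated by tens of points. The documents do not support that. Section 10.0 names Kaplan-Meier only for OS and event-free survival, the sole method described for time to first chemoimmunotherapy is the O/E ratio, and the lag, f and exponential shape are all assumptions. Nor is the treatment failure behind the 27-month figure defined.

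**Conclusion.** The inconsistency is real and should be reconciled, at minor severity. Under 7.1 and 7.3, progression causes no bias. Under a literal 9.1 without later dates, and provided some patients start therapy after progression, time to next therapy is overstated and observed events are undercounted, both favouring ofatumumab. The direction does not depend on the assumed values. The size does: the 1-to-61-point range is illustrative only, and the observed-count fractions should not be read as O/E ratios, which are attenuated less if expected events also stop at removal.

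The OS gap is a separate minor matter. OS is not a listed objective, and its bias is zero if the death hazard does not change after therapy. The primary endpoint, the sample size of 44 and the stopping rules are unaffected.

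**What to change.** Three wording changes, none touching a treatment rule:

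1. In Section 9, state for data collection only that progression does not end follow-up, and refer to 7.1 and 7.3 for when it does.
2. Require the date and type of next CLL therapy for every patient, regardless of progression.
3. Either collect vital status after next therapy by record review or telephone, or delete OS from Section 10.0.

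The cost is a short amendment and a small amount of chart review or telephone contact. No visits or procedures are added, and all visits are already at one center.
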